Results from the toxicokinetics data collected in the 6 month repeat IV dose study showed that after the last dose (Dose 14) the mean half-life was 499 hours (21 days and 547 hours (23 days for the 10 and 100 mg/kg groups, respectively). There were no anti-MEDI-545 antibodies detected in any of the IV monkey studies. Comparison of toxicokinetics at the 100 mg/kg SC dose from the single SC dose study and the single IV dose study demonstrated satisfactory bioavailability by the SC route. The SC C_{max} was 1576.3 $\mu\text{g/mL}$ compared to the 2235 $\mu\text{g/mL}$ for IV. Half-life was comparable (278 hours for SC vs. 368 hours for IV) as was $AUC_{(0-\infty)}$ (513753 $\mu\text{g}\cdot\text{hr/mL}$ for SC and 492508 $\mu\text{g}\cdot\text{hr/mL}$ for IV). There were no anti-MEDI-545 antibodies detected in the single SC dose study. Toxicokinetics analysis in the repeat SC dose study after the last dose (Dose 4) showed a mean half-life of 352 hours (14.7 days) and 368 hours (15.33 days) for the 10 and 100 mg/kg dose groups, respectively. Immunogenicity assay results showed evidence of anti-MEDI-545 antibody at Study Day 106 (Recovery Phase Day 78) in one high-dose male and one control female (the control animal's positive assay outcome could be a result of the immunogenicity assay's expected 5% false positive rate).

Following single-dose SC administration of MEDI-545 (10, 30, and 100 mg/kg), toxicity was assessed based on mortality, clinical observation, dermal irritation, body weight, ophthalmologic, electrocardiographic, blood pressure, clinical pathology, organ weight, and macroscopic and

microscopic pathology data. Immunogenicity assay results found no anti-MEDI-545 antibody detected at any time point for any animal. There were no treatment-related effects in any of the parameters assessed. The NOAEL for this study was determined to be at least 100 mg/kg, the highest dose tested.

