- t. Photographs of up to two target skin lesions (if present) are requested. One photograph should be of the skin lesion that will be biopsied. It is preferred that the photographs are taken prior to the punch skin biopsy.
- u. Flow cytometry will be performed on peripheral blood samples from selected sites in North America.
- v. On Study Days 0, 98 and 182 only, serum samples for MEDI-545 concentrations are collected immediately before, immediately after (within 10 minutes after the infusion has stopped), and 2 hours after administration of the IV infusion.
- w. Open muscle biopsy, unless otherwise approved by the sponsor.

Table 5 Schedule of Patient Evaluations (Follow-up Period)

Study Day Visit	Follow-up Period								
	185	189	196 ^a	210	238	266	294	322	350 ^b
	15	16	17	18	19	20	21	22	23
SAFETY ASSESSMENT									
Physical Examination			X						X
Body Weight			X						X
ECG			X						X
Urine βHCG						X			X
Vital Signs ^c	X	X	X	X	X	X	X	X	X
Assessment of AEs/SAEs	X	X	X	X	X	X	X	X	X
Serum Chemistry ^d			X	X	X	X	X	X	X
CBC & Differentials, Platelets			X	X	X	X	X	X	X
Urinalysis			X	X	X	X	X	X	X
Viral Surveillance Testing			X			X			X
Record Concomitant Medications			X	X	X	X	X	X	X
DISEASE ACTIVITY AND DAMAGE									
Serum Levels of Muscle Enzymes ^f			X	X	X	X	X	X	X
Strength in MMT			X		X		X		X
Extramuscular Activity Assessment (MDAAT)			X		X		X		X
Pulmonary Function Tests ^g			X						X
Physician Global Activity Assessment ^h			X		X		X		X
CLINHAQ ⁱ			X		X		X		X
Patient Global Activity Assessment ⁱ			X		X		X		X
Myositis Damage Index			X						X
SF-36v2			X						X
WPAI:SHP Questionnaire			X		X		X		X
Pruritus VAS ^j			X		X		X		X
CDASI ^j			X		X		X		X
DLQI ^j			X		X		X		X
Skin Photographs ^{j,k,l}			X		X		X		X
CORRELATIVE STUDIES									
Serum for Exploratory Research and Storage			X		X		X		X
Serum for Autoantibodies			X						X
Whole Blood for IFN Gene Expression Analyses			X		X		X		X
Peripheral Blood for Flow Cytometry ^m			X		X		X		X
PK/IM									
MEDI-545 Serum Level	X	X	X	X	X	X	X	X	X
Anti-MEDI-545 Antibodies			X		X		X		X

Table 5 Footnotes:

- a. If a patient discontinues after Study Day 98 and prior to Study Day 196, the evaluations scheduled for Study Day 196 must be completed. If a particular assessment has been performed within 2 weeks before the discontinuation visit, it need not be repeated.

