 16. Post-dose blood collection (within 10 minutes after the infusion has stopped and 2 hours after study drug administration)
 - MEDI-545 serum level
 17. AE/SAE assessment

Study Days 14, 42, 70, 84, 112, 140, 168 (\pm 3 Days): Treatment Period

Visits 2, 4, 6, 7, 9, 11, 13

1. Record concomitant medications

2. Urinalysis includes collection of urine for β HCG (for women who are sexually active and are not surgically sterile or at least 2 years postmenopausal)
3. Blood collection
 - Chemistry panel
 - CBC with differential and platelet count
 - Serum levels of muscle enzymes
 - MEDI-545 serum level
 - Whole blood for DNA sample on Study Day 14 only (optional)
4. ECG (Study Days 42, 98, and 140)
5. Vital signs up to 30 minutes before administration of study drug
6. Administration of study drug
7. Monitor vital signs approximately every 15 minutes during administration of the drug, immediately after the infusion (within 10 minutes after the infusion has stopped), and approximately every 30 minutes after the completion of the infusion until stable. Measure blood pressure and heart rate prior to discharge from the site.
8. AE/SAE assessment

Study Days 28, 56, 126, 154 (\pm 3 Days): Treatment Period

Visits 3, 5, 10, 12

1. Record concomitant medications
2. Urinalysis includes collection of urine for β HCG (for women who are sexually active and are not surgically sterile or at least 2 years postmenopausal)
3. Baseline blood collection
 - Chemistry panel
 - CBC with differential and platelet count
 - Serum levels of muscle enzymes
 - Serum for exploratory research (including IFN- α assay and proteomics) and storage
 - Whole blood for IFN gene expression analysis
 - MEDI-545 serum level
 - Anti-MEDI-545 antibodies
4. Viral surveillance testing
5. Disease activity assessments:
 - MMT
 - Extramuscular activity assessment
 - Physician global activity assessment (included as part of MDAAT)
 - CLINHAQ (includes Patient global activity assessment)
 - Pruritus VAS (DM patients only)
 - CDASI (DM patients only)
6. Skin photographs (optional, DM patients only, within 7 days of the visit)
7. Vital signs up to 30 minutes before administration of study drug
8. Administration of study drug
9. Monitor vital signs approximately every 15 minutes during administration of the drug, immediately after the infusion (within 10 minutes after the infusion has stopped), and

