5.4.2 Secondary Endpoints

The secondary endpoints of the study are the PK and IM of multiple IV doses of MEDI-545 and evaluations of disease activity. PK parameters such as peak concentration (C_{\max}), time to peak concentration (T_{\max}), area under the concentration curve within a dosing interval (AUC_{τ}) after the first dose will be estimated. PK parameters at steady state such as peak concentration ($C_{ss, \max}$) and trough concentration ($C_{ss, \min}$) at steady state, time to peak concentration at steady state ($T_{ss, \max}$), area under the concentration curve within a dosing interval at steady state ($AUC_{ss, \tau}$), total body clearance at steady state (CL_{ss}), steady state volume of distribution (Vd_{ss}), terminal phase volume of distribution (Vd_z) and terminal phase half-life ($T_{1/2}$) will also be estimated. All PK parameters will be estimated by non-compartmental analysis. The highest observed concentration will be recorded as C_{\max} and the time to C_{\max} will be recorded as T_{\max} . Terminal phase elimination rate constant (λ_z) will be estimated by regression of the linear portion of the post-absorption serum concentration-time profile after the last dose and $T_{1/2}$ will be estimated as the ratio of natural log and λ_z . The area under the curve within a dosing interval will be estimated using the linear trapezoidal rule. Total body clearance at steady state (CL_{ss}) will be estimated as the ratio of dose and $AUC_{ss, \tau}$. Steady state volume of distribution will be estimated as the product of mean residence time (MRT) and CL_{ss} . Terminal phase volume of distribution will be estimated as the ratio of CL_{ss} and λ_z . Accumulation to steady state will be assessed as the ratio of $C_{ss, \max} : C_{\max}$ and $AUC_{ss, \tau} : AUC_{\tau}$.

MEDI-545 IM will be analyzed by summarizing the number and percentage of PM/DM patients who develop detectable anti-MEDI-545 antibodies by treatment and dose cohort.

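### First-dose AUC rests on one straight line from 2 hours to Day 14, so the AUC accumulation ratio is biased low if the better-sampled Day 182–196 interval is its numerator

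*Protocol*

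**What the plan says.** Section 5.4.2 makes PK a secondary endpoint: "The secondary endpoints of the study are the PK and IM of multiple IV doses of MEDI-545". It fixes the method, "All PK parameters will be estimated by non-compartmental analysis", and the integration rule, "The area under the curve within a dosing interval will be estimated using the linear trapezoidal rule". That rule covers both AUCtau after the first dose and AUCss,tau. It then says "Accumulation to steady state will be assessed as the ratio of" two pairs: Css,max to Cmax, and AUCss,tau to AUCtau.

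The sampling is in section 3.5. Table 4, footnote v, sets the rule for Days 0, 98 and 182: "serum samples for MEDI-545 concentrations are collected immediately before, immediately after (within 10 minutes after the infusion has stopped), and 2 hours after administration". At other dosing visits there is a single pre-dose sample, and the first of these visits is Day 14 ("Study Days 14, 42, 70, 84, 112, 140, 168"). Table 5 adds serum levels on Days 185, 189 and 196.

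Section 5.4.2 does not say which dosing interval supplies AUCss,tau. Days 182–196 is the natural reading: it is the only interval with samples between 2 hours and the next trough, and the terminal rate constant is also taken after the last dose.

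**The concern.** The linear trapezoid lies above any convex falling curve, and the excess grows with the width of the segment. After dose 1 one segment covers almost the whole 14 days. After the last dose the same stretch is cut at 3 and 7 days. The denominator of the accumulation ratio is then overstated more than the numerator, and the ratio comes out too low.

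How much depends on curvature. With a slow single exponential it hardly matters. With a distribution phase in the first days, the straight line from 2 hours to Day 14 passes well above the true curve. What is at stake is the reported first-dose exposure and one of the two planned accumulation measures.

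**Working it through.** The protocol states no AUC or accumulation ratio for this study, so there is no figure of its own to reproduce.

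**Inputs from the protocol.** Dosing every 14 days, 14 doses (3.4.2); infusion of at least 60 minutes (3.4.4), taken as 1 hour; human half-life 15–18 days with linear kinetics (4.9); sampling times as above.

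**Grids.** First dose: end of infusion, 2 h, 14 d. Last dose: end of infusion, 2 h, 3 d, 7 d, 14 d.

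**Case A, mono-exponential, 15-day half-life** (hand version, instantaneous input, C0 = 1):
- k = ln 2/15 = 0.04621 per day. Concentrations: 0.99616 at 2 h, 0.87055 at 3 d, 0.72363 at 7 d, 0.52365 at 14 d.
- True AUC = (1 − 0.52365)/0.04621 = 10.308.
- First-dose grid: 0.0832 + 13.9167 × (0.99616 + 0.52365)/2 = 10.659, or +3.4%.
- Last-dose grid, same curve shape: 0.0832 + 2.7223 + 3.1884 + 4.3655 = 10.359, or +0.5%.
- Effect on the ratio: 1.005/1.034 = 0.972, or −2.8%.

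With the 1-hour infusion simulated, the ratio reads 2.04 against a true 2.10 (−2.8%) for 15 days and 2.35 against 2.40 (−2.0%) for 18 days.

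**Case B, one worked bi-exponential example.** Assumed, not in the protocol: 40% of the peak declines with a 2-day half-life, the rest with a 15-day half-life.
- First dose: true AUC = 0.4 × 0.99219/0.34657 + 0.6 × 10.308 = 7.330. Concentrations are 0.9863 at 2 h and 0.3173 at 14 d. Linear rule: 0.0828 + 13.9167 × (0.9863 + 0.3173)/2 = 9.154, or +25%.
- Steady state: true AUC = 0.4/0.34657 + 0.6/0.04621 = 14.138. Concentrations at 0, 2 h, 3, 7 and 14 d are 1.6627, 1.6464, 1.2391, 0.9471 and 0.6627. Linear rule: 0.138 + 4.208 + 4.372 + 5.634 = 14.353, or +1.5%.
- True ratio 14.138/7.330 = 1.93; planned ratio 14.353/9.154 = 1.57. With the infusion simulated the bias is −18.5%.

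**Range.** Over fast shares of 30–65%, fast half-lives of 1–4 days and terminal half-lives of 15–18 days, the bias runs from −8% to −41%, downward throughout.

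**Is a fast phase plausible?** Section 1.3 gives, for a single 100 mg/kg IV dose in monkeys, Cmax 2235 µg/mL and AUC 492,508 µg·h/mL, and says "Half-life was comparable (278 hours for SC vs. 368 hours for IV". A single exponential would give 2235 × 368/ln 2 = 1,186,588. The stated AUC is 492,508/1,186,588 = 41.5% of that, which suggests a substantial fast phase in that species.

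**What the same grid does.** In the Case B example, log-down on 2 h to 14 d for both intervals:
- First dose: 0.083 + 13.9167 × (0.9863 − 0.3173)/ln(0.9863/0.3173) = 8.292.
- Steady state: 0.138 + 13.9167 × (1.6464 − 0.6627)/ln(1.6464/0.6627) = 15.182.
- Ratio 15.182/8.292 = 1.83 against 1.93, or −5%.

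Over the full range this leaves 0% (mono-exponential) or about −1% to −15%. Log-down without matching the grids still leaves −3% to −30% in the bi-exponential cases.

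**The case against.** Four points on the other side deserve weight.

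- **The only human PK figure shown gives a trivial error.** With a 15–18 day half-life and no distribution phase, the bias is 2–3%. The larger range rests on assumed parameters. The monkey figures are summary values at ten times the top dose here, and the same check on the SC data is milder: 1576.3 × 278/ln 2 = 632,205 against a stated 513,753, or 81%. SC absorption blunts a distribution phase, so this does not rule one out, but it warns against carrying the 41.5% over to patients. This stands.
- **The numerator is inferred.** Day 98 is sampled like Day 0, with the next draw on Day 112, so the plan already permits a matched ratio for patients on active drug from Day 0. Under the linear rule that ratio has no bias if decline is mono-exponential, and −4% to −19% with a fast share of 30–60% and a fast half-life of 1–3 days. This stands, and is why the interval should be named.
- **Other measures are sound.** Css,max:Cmax uses identical peak sampling. CLss is off by only about −0.3% to −3.3% over that same narrower range if it uses Days 182–196. Troughs at every dosing visit show the approach to steady state. No decision rule in the protocol uses the AUC ratio. This limits the harm. However, the peak ratio does not estimate AUC accumulation: in the worked example it is 1.66, against an AUC ratio of 1.93.
- **An analysis plan may refine the method.** It could change the integration rule or add a model. It cannot supply the missing first-interval samples, and section 5.4.2 as written fixes the linear rule.

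A reader might go further and infer that the study would report almost no accumulation for a drug that roughly doubles. The documents do not support that. Readings below 1.2 need a 65% fast share, a 1–2 day fast half-life and a 15-day terminal half-life together. Case A reads 2.04 to 2.35.

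**Conclusion.** The point holds conditionally. The sampling gap, the linear rule and the accumulation ratio are all in the protocol. If AUCss,tau comes from Days 182–196, the direction of bias is downward for any convex decline. Its size is not established: negligible on the documented half-life alone, material only with a distribution phase, which the monkey data make plausible but do not quantify for patients. It concerns a descriptive secondary result, not safety conclusions or dose escalation. It merits correction because the remedy is cheap and the present text leaves the key interval undefined.

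**What to change.** Amend section 5.4.2 as follows.

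1. Name the dosing interval that supplies AUCss,tau.
2. For the accumulation ratio only, compute both AUCs by linear-up/log-down on the same grid: end of infusion, 2 h and Day 14 of the interval. AUCss,tau for CLss can keep all samples.
3. Report the trough ratio beside it. It needs no AUC, but it reflects terminal-phase accumulation and can sit above the AUC ratio (0.6627/0.3173 = 2.09 against 1.93 in the worked example), so it supports the AUC ratio and does not replace it.
4. Describe first-dose AUCtau as approximate. Where possible, support it with a two-compartment (population) fit to the concentrations already planned: pre-dose levels, Days 0, 98 and 182, and follow-up to Day 350. Patients first given placebo have the same gap after their first active dose, from Day 98 to Day 112, and the same wording should cover them.

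The cost is some PK analysis time and one paragraph. A residual bias of up to about −15% remains possible in the non-compartmental ratio, and the text should say so. No samples or visits are added.

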Extramuscular Activity Assessment (MDAAT)		X	X ^c	X		X				X		X		X		
Pulmonary Function Tests ⁿ		X								X ^o						
Physician Global Activity Assessment ^p		X	X ^c	X		X				X		X		X		
CLINHAQ ^q		X	X ^c	X		X				X		X		X		
Patient Global Activity Assessment ^q		X	X ^c	X		X				X		X		X		
Myositis Damage Index			X ^c							X						
SF-36v2			X ^c							X						
WPAI:SHP Questionnaire			X ^c							X						
Pruritus VAS ^r			X ^c	X		X				X		X		X		
CDASI ^r			X ^c	X		X				X		X		X		
DLQI ^r			X ^c							X						
Skin Photographs ^{r,s,t}			X ^c	X		X				X		X		X		

Table 4 Schedule of Patient Evaluations (Screening and Treatment Period)

Study Day	Visit	Screen ^b	Treatment Period													
			0	14	28	42	56	70	84	98 ^a	112	126	140	154	168	182
			1	2	3	4	5	6	7	8	9	10	11	12	13	14
CORRELATIVE STUDIES																
Serum for Exploratory Research and Storage ^{j, s}			X ^b		X		X			X		X		X		
Serum for autoantibodies ^j			X ^b							X						
Whole Blood for IFN Gene Expression Analyses		X	X ^b		X		X			X		X		X		
Peripheral Blood for Flow Cytometry ^{j, u}			X ^b							X						
Muscle Biopsy ^w			X ^b							X						
Punch Skin Biopsy ^{r, s}			X ^b							X						
Whole Blood for DNA Sample ^s				X												
PK/IM																
MEDI-545 Serum Level ^j			X ^v	X	X	X	X	X	X	X ^v	X	X	X	X	X	X ^v
Anti-MEDI-545 Antibodies ^j			X		X		X			X		X		X		

Table 4 Footnotes:

- a. If a patient discontinues his or her participation in the study prior to Study Day 98, the assessments designated for Study Day 98 will be performed at the discontinuation visit. If a particular assessment has been performed within 2 weeks before the discontinuation visit, it need not be repeated, except if follow-up muscle and skin biopsies have been done at any time, they need not be repeated. (If a patient discontinues after Day 98, see Table 5 footnotes a and b.)
- b. Obtain within 28 days prior to Study Day 0.
- c. Assessments may be performed up to 72 hours prior to dosing on Study Day 0, except muscle and skin biopsies and skin photographs, which may be performed up to 28 days prior to Study Day 0. The open muscle biopsy may be done as part of screening to meet inclusion criteria as long as the dose(s) of immunosuppressive medications have been stable for one month and will remain the same as that in Day 0.
- d. Medical history includes history of viral reactivation events.
- e. Chest x-ray taken within 6 months of screening is considered suitable for screening and need not be repeated.

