- f. Do not administer TB skin test if the patient is known to be positive.
- g. Women, unless surgically sterile or at least 2 years postmenopausal, must have a negative serum pregnancy test within 28 days before randomization/entry, and a negative urine pregnancy test on all dosing visits before receiving the study drug.
- h. Vital signs include heart rate, blood pressure, respiratory rate and temperature. Blood pressure should be obtained with the patient in the position to be used for drug administration. Vital signs will be monitored up to 30 minutes before dosing, approximately every 15 minutes during administration of the drug, immediately after the infusion (within 10 minutes after the infusion has stopped), and approximately every 30 minutes after the completion of the infusion until stable, as judged by the investigator. Blood pressure and heart rate will also be taken prior to discharge from the site on visits in which study drug is administered.
- i. Includes Na, K, Cl, bicarbonate, BUN, creatinine, bilirubin, alkaline phosphatase, and random glucose.

- j. Obtained prior to study drug administration, where applicable. Viral surveillance includes testing for EBV, CMV, HSV, and HPV. The patient will provide self-collected vaginal swabs for HSV and HPV testing; the swabs may also be collected by an MD/OBGYN or qualified medical personnel such as an appropriately trained nurse practitioner, if approved by the sponsor.
- k. A serum sample for assessment of safety biomarkers (including serum levels of mast cell tryptase, cytokines/chemokines, and IgE antibodies) will be collected in all patients prior to study drug administration on Study Day 0 and in any patient with a Grade 1 or higher infusion reaction as soon as possible after the event, 60 minutes after the event, and at discharge (see Section 3.4.4 for details).
- l. At selected sites only.
- m. Serum muscle enzymes include CK, aldolase, AST, ALT, and LDH.
- n. Pulmonary function tests, a part of MDAAT, will assess lung volumes and diffusion capacity for carbon monoxide (DLCO).
- o. Pulmonary function test on Study Day 98 should be done within 7 days before the visit.
- p. Physician Global Activity Assessment is included as part of MDAAT.
- q. Patient Global Activity Assessment is included as part of CLINHAQ.
- r. DM patients only.
- s. Optional procedures.

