3.6.4 Pharmacokinetic, Pharmacodynamic, and Immunogenicity Determinations

All PK and IM laboratory evaluations on samples from North American sites will be performed by MedImmune. MEDI-545 serum concentrations and anti-MEDI-545 antibody detection will be measured by ELISA or ECLA (electrochemiluminescent assay). Sera that are collected may be used for additional PK analyses (MEDI-545 characterization) and MEDI-545 antibody analyses.

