4.9 Dose Escalation

The rules for dose escalation are as follows:

Dose Cohort 1 (single-dose, 0.3 mg/kg or placebo) will be started first. Dosing at each next higher dose cohort (Dose Cohort 2 [1.0 mg/kg or placebo], Dose Cohorts 3A and 3B [3.0 mg/kg or placebo], and Dose Cohort 4 [10.0 mg/kg or placebo] will commence after the Medical Monitor has reviewed the safety information including data through Study Day 42 from the first randomized 8 patients in each of the preceding lower dose cohorts and all cumulative safety data available in all cohorts, and has determined that the safety profile is acceptable (ie, Dose Cohort 2 will start only after safety data from the 8 patients in Dose Cohort 1 has been reviewed and it has been deemed safe; likewise, Dose Cohorts 3A and 3B will start only after the data from the 8 patients in Dose Cohort 2 has been reviewed and it has been deemed safe; Dose Cohort 4 will start only after safety data from the 8 patients from Dose Cohort 3A have been reviewed and it has been deemed safe). Dose Cohorts 3B and 4 will enter patients in parallel.

Available PK data from study MI-CP126 indicated that MEDI-545 has a serum half-life of 15 to 18 days and a linear increase in serum concentrations with dose. As such, the serum MEDI-545 concentration at Study Day 42 is anticipated to be near steady state.

The SMC will independently review cumulative safety surveillance data throughout the study and make recommendations regarding the study progression. The SMC can stop study entry and dosing as it deems necessary.

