5.3 Patient Populations

The patient population analyzed will include all patients who receive at least one dose of study drug.

Safety results will be analyzed in all patients who receive any study drug. Evaluability for analyses of MEDI-545 serum concentrations and PK parameters will be determined based upon the frequency and timing of the serum samples obtained. IM analysis will be performed in all patients who have received at least one dose of MEDI-545. Efficacy results will be analyzed in all randomized patients who receive any study drug.

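### The antibody rate by dose cohort takes no account of drug in the sample, so it can understate immunogenicity at high dose if the assay's drug tolerance is below the high-dose trough

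*Protocol*

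**What the plan says.** Section 5.4.2 makes immunogenicity a secondary endpoint, summarised as the number and percentage of patients "who develop detectable anti-MEDI-545 antibodies by treatment and dose cohort". Section 5.3 sets the denominator: "IM analysis will be performed in all patients who have received at least one dose of MEDI-545". That section ties evaluability for the pharmacokinetic analyses to how often and when serum was drawn, but sets no such condition for immunogenicity.

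The row "Anti-MEDI-545 Antibodies" in Tables 4 and 5 (Section 3.5) gives Day 0 and then Days 28, 56, 98, 126, 154, 196, 238, 294 and 350. The visit lists agree, for example the one headed "Study Days 28, 56, 126, 154". Footnote j to Table 4 says of treatment-period samples: "Obtained prior to study drug administration, where applicable". The last infusion is on Day 182.

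Section 3.6.4 says "anti-MEDI-545 antibody detection will be measured by ELISA or ECLA" and gives no drug tolerance. Section 4.9 reports that "MEDI-545 has a serum half-life of 15 to 18 days and a linear increase in serum concentrations with dose". Section 3.7 lets patients leave for MI-CP212 from Day 266, with the Day 350 evaluations done at the last visit if possible.

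**The concern.** An immunoassay for antibody to a drug can lose sensitivity when the drug is in the sample. Most of the planned samples are taken with drug present, and the amount rises in proportion to dose. A patient who is never positive stays in the denominator, whether antibody was absent or merely hidden. If hiding occurs, it occurs most in the highest cohort, so a lower rate there could be read as lower immunogenicity. The summary by dose cohort is the protocol's stated answer to its secondary immunogenicity objective, and as worded it cannot separate the two explanations.

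**Working it through.** **Plan's own figure.** The protocol states no antibody rate to reproduce. Its relevant figure is the precision in Table 8: for 0 of 6, the 95% upper limit is 1 − 0.025^(1/6) = 45.9%, as printed.

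**Count of samples.** For patients on MEDI-545 from Day 0 there are nine post-dose samples. Infusions are every 14 days from Day 0 to Day 182, so Days 28, 56, 98, 126, 154 and 196 each fall 14 days after an infusion: 6 of 9. Days 238, 294 and 350 fall 56, 112 and 168 days after the last one. Placebo-first patients start MEDI-545 on Day 98 and have six later samples, three of them (Days 126, 154, 196) at trough.

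**Relative drug level.** Inputs: half-life 15 to 18 days and dose linearity (Section 4.9). The pre-dose level at time t is the sum over earlier infusions of dose × 2^(−(t − infusion day)/half-life). Dividing by the 0.3 mg/kg level on Day 196 removes the need for a volume. The ratio between the extreme cohorts is 10/0.3 = 33.3 at every visit.

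| Day | Days since infusion | 0.3 mg/kg (half-life 15 / 18 d) | 10 mg/kg (15 / 18 d) |
|---|---|---|---|
| 28 | 14 | 0.73 / 0.66 | 24.2 / 22.0 |
| 56 | 14 | 0.92 / 0.88 | 30.8 / 29.5 |
| 98 | 14 | 0.99 / 0.98 | 33.0 / 32.6 |
| 196 | 14 | 1 / 1 | 33.3 / 33.3 |
| 238 | 56 | 0.14 / 0.20 | 4.8 / 6.6 |
| 294 | 112 | 0.011 / 0.023 | 0.36 / 0.77 |
| 350 | 168 | 0.0008 / 0.0027 | 0.03 / 0.09 |

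Days 126 and 154 are within 1% of Day 196. Only Days 294 and 350 give the top cohort less drug than the lowest cohort carries at its Day 196 trough. On Day 266, the earliest exit to MI-CP212, the 10 mg/kg level is still 1.3 to 2.25 on this scale, and that visit has no scheduled antibody sample of its own.

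**Absolute scale, on assumptions.** Assume a distribution volume of 50 to 100 mL/kg, which the protocol does not give. The steady-state trough is (dose/volume) × r/(1 − r), with r = 2^(−14/half-life), so r/(1 − r) is 1.10 at 15 days and 1.40 at 18 days.
- 0.3 mg/kg: 3 × 1.10 = 3.3 to 6 × 1.40 = 8.4 ug/mL.
- 10 mg/kg: 100 × 1.10 = 110 to 200 × 1.40 = 280 ug/mL.

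Samples out of nine with drug at or below an assumed tolerance:

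| Tolerance (ug/mL) | 0.3 mg/kg | 10 mg/kg |
|---|---|---|
| 1 | 2 to 3 | 1 |
| 10 | 9 | 2 |
| 50 | 9 | 2 to 3 |
| 100 | 9 | 3 to 4 |
| above 280 | 9 | 9 |

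At 100 ug/mL the 1 and 3 mg/kg cohorts also have 9 of 9, so only the top cohort is affected.

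**Possible size.** Suppose the assay fails above the 0.3 mg/kg trough. Let f be the share of antibody-positive patients who are still positive and sampled on Day 294 or 350. The observed rate at 10 mg/kg is the true rate × f. For an assumed true rate of 20% in every cohort, it is 0% (f = 0), 10% (f = 0.5), 16% (f = 0.8) or 20% (f = 1), against 20% at 0.3 mg/kg.

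**The case against.** A reader might infer that the comparison is biased whatever the truth, so that the top cohort must look least immunogenic. The documents do not support that. No drug tolerance is stated, and above the high-dose trough the effect is nil. The endpoint also counts antibody at any time point: Days 294 and 350 are 112/18 = 6.2 to 168/15 = 11.2 half-lives after the last dose, so persistent antibody in a patient sampled then could still be found and counted.

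A reader might also take the monkey data in Section 1.3 as evidence of masking, since antibody in the repeated subcutaneous study was seen in the recovery phase. One of the two positive animals was a control, the protocol points to an expected 5% false-positive rate as a possible reason, and no antibody was found in any intravenous monkey study. Those data say nothing useful on this point.

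It is fair, too, that Section 5.4.2 labels its count as detectable antibody and nowhere says that a negative proves absence. Handling of drug interference is often set in the analysis plan or the bioanalytical plan, so its absence here is not in itself an error. The summary is descriptive, with six patients per cohort initially on MEDI-545 and eight after crossover, so imprecision limits any dose comparison anyway.

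What stands is that the protocol does fix the numerator, the denominator and the breakdown by dose cohort, and does so without regard to drug level. Small numbers do not remove an effect ordered by dose. The late samples protect only persistent antibody in patients who stay to give them.

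**Conclusion.** The point holds conditionally. The six-of-nine count follows from the schedule, and the 33-fold ratio from the doses and the protocol's statement of linear pharmacokinetics. Whether they distort the by-cohort rate depends on a tolerance that is not stated, so the size runs from no bias to complete masking at the top dose. The exposure is mainly to transient antibody and to patients without Day 294 or 350 samples, including those who leave for MI-CP212. The ratios rest on linear, single-exponential decline with the stated half-life. The interpretability counts rest further on the assumed volume and tolerances. It is worth correcting because the data needed are already collected.

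**What to change.** In Section 5.4.2:
- Keep the planned summary of detectable antibody by treatment and dose cohort.
- Pair each antibody result with the MEDI-545 level from the same visit and state the assay's validated drug tolerance.
- Classify an undetectable result as negative only if that level is at or below the tolerance, and otherwise as inconclusive.
- Report the number interpretable per cohort.
- Show Days 294 and 350 separately as a supporting display. They should not be the sole basis for comparing cohorts, since that would drop transient antibody and lose patients who leave from Day 266. Even Day 294 is not certain to be free of interference: at a tolerance of 1 ug/mL only one of the nine samples at 10 mg/kg qualifies.

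If the analysis plan already contains this rule, a cross-reference is enough. The cost is wording: Tables 4 and 5 already schedule a MEDI-545 level at every antibody visit. The downside is that some on-treatment results become inconclusive. If tolerance proves to exceed the high-dose trough, the rule changes nothing.
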